**NCT05096312**

**Document date: Dec 19, 2018**

## INTRODUCTION

Acne Vulgaris is a common disorder of the pilosebaceous follicles characterized by comedones, papules, pustules, inflamed nodules, canalizing and deep, inflamed sacs usually occurring on areas of the body with hormonally sensitive sebaceous glands, including the face, neck, chest, upper back and upper arms. Moderate to severe acne vulgaris affects around 20% of young people. It persists into the 20s in 64% and into the 30s for 43% of individuals. Lesions last for years, result to permanent scarring, and have serious effects on an individual's psychological health such as depression and social withdrawal. The annual years of healthy life lost per 100,000 people from acne in the Philippines is 50.6 in 2013. This shows that despite the known treatment regimens for acne, Filipino patients are still suffering from the effects of the disease.

Acne has four main pathogenic contributors: follicular hyperkeratinization, increased sebum production, *Propionibacterium acnes* (*P. acnes*) within the follicle, and inflammation. Treatment options for acne vulgaris include benzoyl peroxide, topical and oral retinoids, topical and oral antimicrobials, oral corticosteroids, and physical modalities such as acne surgery, laser and light therapy. Reports show that antibiotic resistance is a growing issue in the treatment regimen of acne vulgaris, making it less and less suitable for long-term treatment, hence other options that can be substitutes or adjuncts to treatment may be useful in this condition. For long-term or maintenance therapy, physicians should consider effectiveness, cost, and adverse effects. Several studies have explored the effect of oral zinc on acne vulgaris. Since zinc is more cost-effective and has less adverse effects compared to most antibiotics, this may prove helpful for the Filipino patient in terms of safety and economy for long-term therapy.

At present, there are no local studies using only oral zinc supplementation as an adjunct for the treatment of acne vulgaris. Thus, this study aims to determine the effect of oral zinc gluconate versus placebo on inflammatory lesions of acne vulgaris in the Filipino population. Furthermore, this study may also be able to provide more information for further studies towards non-antimicrobial treatment regimens for acne vulgaris in the Philippines.

## Review of Related Literature

Acne Vulgaris is one of the most common dermatologic diagnoses affecting approximately 9.4% of the global population making it the eighth most prevalent disease worldwide. A significant number of adult patients continue to develop new-onset acne beyond the teenage years with prevalence found to be at 50-54% in females and 40-42.5% in males. Moreover, the prevalence of acne did not substantially decrease until after the age of 44. Since acne vulgaris is a chronic and persistent skin condition, safe and effective long-term maintenance therapy is often required. Antibiotic resistance in acne vulgaris can occur in *P. acnes* and other organisms, creating an increase in more pathogenic strains of these bacteria. Given the gravity of the consequences of this trend, it is a challenge to maximize use of non-antimicrobial therapy when treating acne. Other options for treatment of moderate to severe acne vulgaris are already being explored. A study by Stein Gold et al has shown that the fixed combination of adapalene 0.3% / benzoyl peroxide 2.5% is an effective and safe single-agent topical therapy for moderate and severe inflammatory acne.

Oxidative status has been implicated in the pathogenesis of several skin diseases, including acne. A study measured oxidative stress by taking plasma levels of catalase (CAT),

superoxide dismutase (SOD), total antioxidant capacity (TAC), and malondialdehyde (MDA). MDA in acne patients were significantly higher as compared with that of the controls, whereas activities of the antioxidant enzymes SOD and CAT were lower. Hence, this suggests that oxidative stress plays a key role in acne vulgaris.

Zinc is present in all body tissues and has been shown to have antioxidant properties. It is an essential element of more than 200 metalloenzymes, including the antioxidant enzyme, superoxide dismutase, and it has the ability to effectively decrease reactive oxygen species, a key factor in oxidative stress. Zinc also contributes to normal epithelial differentiation and development, protects against UV radiation, enhances wound healing, contributes to proper immune, reproductive and neuropsychiatric functions, and may decrease the relative risk of cancer and cardiovascular disease.

The recommended daily allowance (RDA) of zinc is 8 mg elemental zinc for adult females and 11 mg elemental zinc for adult males. The tolerable upper intake level of zinc is 40 mg elemental zinc for both adult males and females. Possible side effects related to oral zinc, usually from zinc sulfate, include nausea, vomiting, abdominal pain and diarrhea. According to Sardana et al, the effervescent preparations and zinc gluconate had better results as compared to zinc sulfate and citrate. Zinc gluconate is better tolerated by the gastric mucosa hence causing much less of the known adverse effects of zinc. Zinc gluconate contains 14% elemental zinc, meaning a 100 mg tablet contains 14 mg elemental zinc.

Data suggest that zinc deficiency exist both in developed and developing countries, and several factors that may affect serum zinc levels include low intake of highly absorbable zinc in fresh foods, high phytate content of some staple food, pregnancy, lactation, and increased demands of physiological processes such as growth and sexual maturation. Whole blood zinc levels were measured from healthy subjects in relation to sex and age using atomic absorption spectrophotometry. Mean level of zinc obtained in whole human blood from males was 607.0 +/- 105.3 micrograms/100 ml and in females 585.2 +/- 122.9 micrograms/100 ml. The results showed that males had slightly higher zinc levels but the difference was not statistically significant.

A few researches have been done in other countries comparing zinc levels in blood with the severity of acne. A study by Saleh done in Iraq measured trace elements in the blood, such as zinc and copper, and correlated it to the severity of acne vulgaris. The results showed that patients with severe acne had significantly lower levels of zinc. As shown in a study done in Iran, zinc levels may be related to the severity and type of acne lesions in patients with acne vulgaris, the relative decrease of serum zinc level in acne patients suggests a role for zinc in the pathogenesis of acne vulgaris. Another study of 173 acne patients published in the British Journal of Dermatology showed that retinol binding protein and serum zinc levels were significantly lower in severe acne. In an unpublished study, a significant relation of whole blood zinc levels with the severity of acne vulgaris was found in Filipinos, with severe acne showing significantly lower zinc levels. Some studies concluded that due to this, it might be helpful to give zinc supplements to acne vulgaris patients.

Zinc is still being studied and was found to have multiple uses in medicine and general dermatology as oral and/or topical therapy for conditions such as warts, cutaneous leishmaniasis, leprosy, herpes genitalis, dermatophytosis, bromhidrosis, pityriasis versicolor, acne vulgaris, rosacea, hidradenitis suppurativa, eczema, ulcers, and alopecia areata. Oral zinc has been

compared to oxytetracycline in a study by Michaelsson et al, and showed no significant difference in the effect on acne vulgaris. On the other hand, a study by Dreno et al showed that minocycline was superior to oral zinc in the treatment of acne vulgaris and a study by Cunliffe et al showed that although oral zinc was correlated with decreased inflammatory lesions, tetracycline has a superior effect. These studies compared oral zinc with antibiotics, which are already established treatment options for acne vulgaris. There are some instances, however, when patients are already resistant to antibiotics or are reluctant to take antibiotics for long-term. Oral zinc for acne vulgaris may be useful for patients who cannot or do not want to take oral antibiotics in the long-term and for those who already have erythromycin- or clindamycin-resistant strains of *Cutibacterium acnes* (*Propionibacterium acnes*). Multiple sources showed that when oral zinc was compared to placebo, there was a significant improvement in inflammation and number of acne lesions. Furthermore, adding zinc salts in vitro to culture media of *Cutibacterium acnes* (*Propionibacterium acnes*) reduced resistance of the bacteria to erythromycin. One of the anti-inflammatory effects of oral zinc in acne was found to be in the inhibition of TLR2 surface expression by keratinocytes. Studies about giving oral zinc gluconate supplements versus placebo in the Philippine setting have not yet been done.

The inflammatory score is a grading system that measures inflammatory lesions only. It includes locations such as the face, chest and back. For each location, papules, pustules and nodules are counted. A factor based on the lesion (papule=3, pustule=4, nodule=5) is used to be multiplied to a grade equivalent to the number of lesions. The subtotal scores are added with a maximum possible total score of 144.

The Global Acne Grading System (GAGS) is an acne severity scale that includes six locations on the face, chest, and back. A factor based on surface area and distribution of pilosebaceous units is provided for each of the six locations, and grades are based on the type of lesions per area (1 for  $\geq$  one comedone, 2 for  $\geq$  one papule, 3 for  $\geq$  one pustule, and 4 for  $\geq$  one nodule). The factor and the grade are multiplied to get a local score. The local scores are then added with a maximum possible global score of 44. Acne severity is rated as mild, moderate, severe, and very severe with corresponding cut-off scores.

### **Research Question**

Does oral zinc gluconate supplementation improve inflammatory acne as measured by the inflammatory score and GAGS score in diagnosed acne vulgaris patients?

### **Objectives**

#### **GENERAL**

- To assess the efficacy of oral zinc gluconate in the improvement of disease activity in diagnosed acne vulgaris patients.

#### **SPECIFIC**

- To determine the demographic and clinical profile of Acne Vulgaris patients
- To determine the disease activity measured by the inflammatory score and GAGS score of acne vulgaris patients on initial consult, at 4 weeks, and at 8 weeks.
- To determine if there is a significant difference in disease activity as measured by the inflammatory score and GAGS score among acne vulgaris patients given placebo and oral zinc gluconate.

## **METHODOLOGY**

### **Study Design**

A randomized, double blind, placebo-controlled clinical trial was utilized for this study which was conducted from December 2018 to July 2019.

### **Ethical Considerations**

The protocol will be submitted for ethical review and approval by the Technical Review Board and Institutional Ethics and Review Board of the East Avenue Medical Center. Informed consent will be obtained from the participants prior to participation in the study. All data collection will be done in a setting that ensures patient safety and privacy. Patient will be assured of the confidential nature of the patient-provider interactions. Active listening, open-ended questions and clarifications will be used.

The investigators will perform physical examination of the patient to assess the severity classification, and any photographs that will be taken of the patient or the skin lesions will be subject to informed consent. No closed-circuit television or recording devices will be used in the rooms for interview and physical examination.

### **The Informed Consent Process:**

Informed consent will be obtained from the participants prior to participation in the study. At the onset, patient will be assured of the confidential nature of the patient-provider interaction. The investigator will explain that to ensure confidentiality in data collection, the investigators will assign a code to replace patient identifiers (e.g. name). Only authorized members of the research team will be allowed to access the result. All pertinent records will be stored in a locked cabinet. The records identifying the subject will be kept confidential and will not be made publicly available. In obtaining and documenting informed consent, the investigator adheres to Good Clinical Practice guidelines and to sound ethical principles. During the procurement of the informed consent, the investigator will go through the informed consent form which will include the following: that the patient will enter into a research study, the purpose of the study, the procedure to be followed, the possible risks involved (skin irritation from the topical medications and nausea from the oral zinc) and the expected benefits (patient will be provided with free medications). The subject will also be provided contact details of whom to speak to if she or he has any questions or any concerns regarding the study. The investigator will not coerce or unduly influence a subject to participate or to continue to participate in a trial without their consent. It will be emphasized that whether the patient chooses to participate or not participate in the study, he or she will still receive appropriate treatment. It will also be made clear that no compensation will be given for participating in the study. None of the oral and written information concerning the trial will contain any language that causes the subject to waive or to appear to waive any legal rights or that releases or appears to release the investigator for liability from negligence. Active listening, open-ended questions and clarifications will be used. The investigator will provide the subject with ample time and opportunity to inquire about details of the trial and to decide whether or not to participate in the trial. All questions will be answered to the satisfaction of the subject. By signing the consent form, the subject attests that the information in the consent form and any other written information was accurately explained and apparently understood by the

subject and that informed consent was freely given. At any time during the process, the subject can opt to refuse from participating in the study.

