### **Checking of Compliance**

Participants will be given a Daily Monitoring Sheet where they can note if they have taken

the capsule for the day, as well as side effects or other remarks. The number of remaining capsules will be checked every 2 weeks during follow-up. Patient will be required to bring medicine bottle on follow-up for the pill count.

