### **Stopping Guidelines**

[figure not shown]
Criteria for stopping the intervention include anaphylactic reaction or allergies to the medications, and severe gastrointestinal symptoms. Patients with severe adverse reactions will be treated accordingly to relieve symptoms. They will be considered as "withdrawals" of the study, and still receive proper treatment for acne vulgaris.

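### The risks described for consent are narrower than those the protocol itself names: vomiting, abdominal pain, diarrhea and allergic reaction including anaphylaxis are left out.

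*Combined protocol and SAP*

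**What the plan says.** Three sections of the combined protocol and SAP deal with the harms of the study products.

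- **The Informed Consent Process** says that "the investigator will go through the informed consent form which will include the following", and among the items gives "the possible risks involved (skin irritation from the topical medications and nausea from the oral zinc". It names no further risk. It also says: "The subject will also be provided contact details of whom to speak to if she or he has any questions or any concerns".
- **Review of Related Literature** says: "Possible side effects related to oral zinc, usually from zinc sulfate, include nausea, vomiting, abdominal pain and diarrhea". It then qualifies this for the salt used in the trial: "Zinc gluconate is better tolerated by the gastric mucosa hence causing much less of the known adverse effects of zinc".
- **Stopping Guidelines** says: "Criteria for stopping the intervention include anaphylactic reaction or allergies to the medications, and severe gastrointestinal symptoms".

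On how symptoms come to light, Checking of Compliance gives participants a daily sheet on which they can record whether they have taken "the capsule for the day, as well as side effects or other remarks". Intervention has the capsules taken at home, and Study Procedure plans follow-up every 2 weeks.

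**The concern.** The consent section states what the form will contain, and its risk statement is shorter than the risks set out elsewhere in the same document. If the form were written to that description, a participant would agree to take part without having seen three of the four gastrointestinal effects that the protocol attributes to oral zinc. Nor would the participant have seen any mention of allergic reaction, although the protocol treats allergy and anaphylaxis as reasons to stop.

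What is at stake is the completeness of disclosure and, secondarily, of safety reporting. Between the 2-weekly visits, side effects are noted by the participants themselves. Outcome Measures lists no safety outcome and none of the dummy tables records adverse events, so participants' own reports carry much of the safety information. The efficacy comparison is not affected.

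**Working it through.** No figure is involved, so the check is a comparison of text. Each reaction the protocol names is set against the consent description.

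| Reaction | Where the protocol names it | In the consent description? |
|---|---|---|
| Skin irritation | The Informed Consent Process (topical) | Yes |
| Nausea | Review of Related Literature (oral zinc) | Yes |
| Vomiting | Review of Related Literature (oral zinc) | No |
| Abdominal pain | Review of Related Literature (oral zinc) | No |
| Diarrhea | Review of Related Literature (oral zinc) | No |
| Severe gastrointestinal symptoms | Stopping Guidelines | Only as far as nausea |
| Allergy, including anaphylaxis | Stopping Guidelines (the medications, product not specified) | No |

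**Gastrointestinal effects.** The literature review lists four and the consent description carries one, so 4 − 1 = 3 are left out.

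**Allergic reaction.** The Stopping Guidelines put anaphylaxis and allergies in one phrase. Anaphylaxis is a severe form of allergy, so the two are treated here as one omitted item. The phrase refers to the medications in general, which can include the adapalene and benzoyl peroxide topical. The consent description omits allergic reaction for both products, so the omission stands whichever one was meant.

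**Is the parenthesis only illustrative?** It does not read that way. The same section uses e.g. when it gives an example of a patient identifier, and the Statistical Analysis Plan does so for its variables. The risk parenthesis has no such marker. It does not say only, either, so an exhaustive list is the more natural reading but not the only possible one.

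**Does the gluconate qualifier explain the short list?** The literature review makes two qualifying statements: the effects usually come from zinc sulfate, and gluconate causes much less of them. Both apply to all four effects alike, so they give no reason to keep nausea and drop the other three. Much less is also not none, and the Stopping Guidelines still provide for severe gastrointestinal symptoms.

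**The case against.** The strongest reply is that the form has not been seen. The consent section summarises the form in a sentence, the form itself was not available for this review, and its risk section may be complete. This stands as a limit on the claim. A reader might infer that participants are not told of these reactions, and the documents do not support that. They support only that the described content is narrower than the protocol's other sections. If the form is fuller, the description needs correcting; if it matches the description, the disclosure needs extending. The sections need reconciling in either case.

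Second, the list of four effects comes from a literature review of oral zinc in general, with the qualifiers noted above. This also stands in part. A shorter summary is incomplete against that list but does not contradict it, and the expected frequency of these effects with gluconate is lower than the bare list suggests.

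Third, other channels exist: an open field for side effects on the daily sheet, contact details for any concern, patient education when the bottle is given, and assessment every 2 weeks. This is fair. A reader might infer that the stopping guideline would act late, or that naming nausea alone would steer what participants record. Nothing in the documents shows either. Nor do they set a duty on participants to report particular reactions; the sheet is somewhere they can note them.

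Fourth, anaphylaxis should not be presented as a known risk of the capsule. Agreed: it appears only as a stopping criterion and is not tied to one product.

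**Conclusion.** The point holds as a gap between sections of the protocol. The consent description carries one of the four gastrointestinal effects listed for oral zinc and says nothing of allergic reaction, including anaphylaxis, which the protocol foresees as a reason to stop.

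The conclusion rests on reading the risk parenthesis as the intended list, which its wording favours but does not prove, and on the protocol text alone. It makes no claim about the content of the form or about harm to any participant. A reader might want to measure the gap by the number of doses taken between visits. That would only restate the dosing schedule: the number would be the same under full disclosure.

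This is an inexpensive improvement to disclosure and safety reporting, not a threat to the trial's efficacy conclusions.

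**What to change.** In The Informed Consent Process, reconcile the risk list with the Review of Related Literature and the Stopping Guidelines. Keep skin irritation and nausea, and add vomiting, abdominal pain, diarrhea, and allergic reaction including anaphylaxis to the study medications, whether capsule or topical. Note there that the Stopping Guidelines list criteria for stopping the intervention. The statement that gluconate is better tolerated can stay alongside the list as context. Then check that the consent form and the Daily Monitoring Sheet carry the same list. Every item is already in the protocol, and no dose or clinical rule changes.

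Study Design describes the trial in the past tense, as conducted from December 2018 to July 2019, while other sections are written in the future tense. If the study has already been conducted, check the form actually used and state any gap when reporting adverse events.

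The cost is a wording change and an ethics-board notification. A longer list may produce slightly more expectation-driven symptom reporting, in both arms.

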### **Study Setting**

The study will be conducted at the Out-patient Clinic and the Skin Center of the East Avenue Medical Center (EAMC) Department of Dermatology. The hospital had adequate staff and infrastructures to provide for the requirements of this study to be conducted properly.

### **Study Population**

The subjects of the study included patients clinically diagnosed with acne vulgaris, aged 18-27 years of age.

